#### 20 mg Tablets in Blister Packs

- Selinexor tablets (20 mg) are currently in ongoing stability studies. The expiry will be based on concurrent stability studies and extended during the course of the study as further stability data becomes available.
- All selinexor tablets must be kept in an appropriate, limited access, secure place until dispensed, destroyed or returned to Karyopharm Therapeutics, Inc. or designee for destruction.
- Selinexor tablets can be stored at room temperature or refrigerated, at or below 86 °F or 30 °C, do not freeze. Room temperature storage is recommended. The study site

will be required to maintain a log of the temperature where the study medication is stored.

Each bottle of selinexor tablets will be labelled in accordance with current International Conference on Harmonisation (ICH) Good Clinical Practice (GCP), FDA and specific national requirements.

Sites must request study drug by submitting an order form directly to the drug depot in order for the study drug to be shipped to the site pharmacy. The Investigator (or designee) will verify and acknowledge receipt of all study drug shipments by signing and returning all required forms.

The Investigational medicinal product should not be used for any purpose outside the scope of this protocol, nor can Investigational medicinal product be transferred or licensed to any party not participating in the clinical study. Karyopharm's data for Investigational medicinal product are confidential and proprietary and shall be maintained as such by the Investigators.

#### **5.4.2 Drug Storage**

Selinexor tablets will be stored at room or refrigerated temperatures between 5-30°C (41-86°F) in a locked and secured area with restricted access. Room temperature storage is recommended. The tablets should not be stored at freezer temperatures or allowed to freeze. Tablets will be supplied in white high-density polyethylene (HDPE) bottles. All medication must be stored in a secure area under the proper storage requirements with access restricted to the site staff pharmacist or designee(s).

#### **5.4.3 Accountability and Destruction of Investigational Medicinal Product**

The Principal Investigator (or an authorized designee) at each participating institution must maintain a careful record of the inventory of the Investigational medicinal product received using the Drug Accountability Form. The study drug will be destroyed as per the institutions destruction policies and documentation of study drug destruction will be provided to Karyopharm. Both used and unused study drug may be returned to Karyopharm if requested.

#### **5.4.4 Drug Administration**

Each dose will consist of selinexor for oral administration on a fixed dose basis. Patients should not receive more than a 70 mg/m^2 dose, so the dose given is subject to a BSA limit (example for 100 mg, a BSA is limited to > 1.43 m^2).

Selinexor doses planned for this study are 80 mg twice weekly and 100 mg twice weekly. Potential de-escalation doses are 60 mg twice weekly and 40 mg twice weekly.

Selinexor tablets are to be taken within 30-minutes of solid food consumption together with at least 120 mL (4 ounces) of fluids (water, milk, etc.). Selinexor tablets should not be crushed because of increased risk of dermatologic toxicity if the powder comes in contact with skin.

#### **(B) Sorafenib administration**

Sorafenib is supplied as an immediate-release film-coated, round, and salmon color tablet containing 200 mg of the free base, Sorafenib, and the excipient croscarmellose sodium, microcrystalline cellulose, hydroxypropyl methylcellulose, sodium lauryl sulfate, and magnesium stearate. The film-coat consists of hydroxypropyl methylcellulose, polyethylene glycol, titanium dioxide and red iron oxide. The film coating has no effect on the rate of release of the active sorafenib.

If sorafenib is administered on a BID schedule, sorafenib drug doses must be separated by intervals of approximately 12 hours (+/-3 hours).

If a dose is missed, the next dose should not be increased to account for missing a dose. The subject should take the next regular dose at the regularly scheduled time. If a dose is vomited, do not take another dose of medication. Wait until the next dose is due. Take the next regular dose and do not increase it to account for missing a dose.

Modifications to the schedule and/or dose of both/either drugs that are thought to be in the best interest of the patient are allowed after discussion with and approval by the PI.

### **5.5 Supportive Care Recommendations for Selinexor-Related Adverse Events**

Supportive measures for optimal medical care should be provided during participation in this clinical trial. Based on clinical observations in over 400 adult patients treated with selinexor as of 01 October 2014, the main side effects are primarily related to anorexia with poor caloric and fluid intake, fatigue, and nausea. Thrombocytopenia also occurs, although it is rarely associated with bleeding.

#### **Required Supportive Care Medication**

*5-HT3 Antagonists*

In order to minimize nausea, unless contraindicated, all patients must receive 5-HT3 antagonists (ondansetron 8 mg or equivalent) starting before the first dose of selinexor and continued twice daily (bid) – three times a day (tid) as needed (prn).

Besides the required 5-HT3, supportive care including anti-nausea / anti-emetic therapy, acid suppression (proton pump inhibitors and/or H2-blockers) and other treatments may be administered as described below:

- Glucocorticoids: dexamethasone (4-12 mg) or equivalent glucocorticoid (e.g., prednisone 10-20 mg) on days of, and 1 day after, selinexor dosing may improve appetite, reduce nausea or vomiting, and minimize fatigue. A maximum of 40 mg dexamethasone or equivalent may be given per week.
- Appetite stimulants: megestrol acetate at a dose of 80-400 mg daily.
- Centrally acting agents: per National Comprehensive Cancer Network® [NCCN] Clinical Practice Guidelines® for antiemesis and anorexia/cachexia [palliative care]).
- NK1R antagonist: aprepitant or equivalent should be considered and will be covered for selected patients who have severe nausea and vomiting.

## 5.6 Concomitant medications

### 5.6.1 Required Concomitant/Supportive Care Medications

- Oral dexamethasone (4 mg) will be given to all patients with each dose of selinexor ( $\pm$ 1 day after) to improve tolerability. Co-administration was found to improve appetite, reduce nausea/vomiting, and minimize fatigue in patients treated with selinexor. Higher doses of dexamethasone (or an equivalent corticosteroids) may be appropriate for short periods of time. For all patients, maximum of 40 mg dexamethasone or equivalent per week is permitted.

#### *5-HT3 Antagonists*

In order to minimize nausea, unless contraindicated, all patients must receive 5-HT3 Antagonists (ondansetron 8 mg or equivalent) starting before the first dose of selinexor and continued twice daily (bid) – three times a day (tid) as needed (prn).

**5.6.2** In general, the use of any concomitant medication/therapies deemed necessary for patient supportive care and safety are permitted. Since the effect of both selinexor and sorafenib may be delayed for up to 4 weeks, patients with high WBC counts may receive hydroxyurea prior to study entry. Hydroxyurea is allowed before the start of study therapy

and for the first four weeks on therapy. Hydroxyurea is allowed after completion of first cycle of treatment to control high WBC with PI approval. Concurrent therapy for CNS prophylaxis or continuation of therapy for controlled CNS disease is permitted as defined in inclusion criteria 4.1.8. With the exception of these agents, concomitant systemic chemotherapy is not permitted.

Concomitant medications are recommended as prophylaxis for nausea, vomiting, and infections, and are allowed for managing myelosuppression as shown in Table 5.

**Table 5: Instructions for the use of concomitant medications and therapies**

Category of Use	Medication	Comment on Use	Restriction on Use
Recommended	Prophylactic antibiotics, antifungal agents, and antiviral agents	Strongly encouraged	None
	Antiemetic agents	According to standard of care at MDACC	None
Allowed	Oral allopurinol or rasburicase	At investigators discretion	None
	Leukapheresis	According to standard of care at MDACC	Before induction 1 day 1 only
	Red blood cell transfusion	None	None
	Platelet transfusion	None	None
	White blood cell transfusion	At investigators discretion according to standard of care at MDACC	None
	Myeloid growth factors or platelet growth factor	At investigators discretion according to standard of care at MDACC	None
	Erythropoietin or darbepoetin	At investigators discretion according to standard of care at MDACC	None
	Any other medication for supportive care	At investigators discretion according to standard of care at MDACC	None

### **5.6.3 Use of Blood Products**

During the administration of selinexor, patients may receive red blood cell (RBC) or platelet transfusions, if clinically indicated, per institutional guidelines.

Myelosuppression is expected in patients with AML due to underlying disease, as well as due to therapies (such as selinexor and sorafenib), or both. Most patients have neutropenia, thrombocytopenia, or both at study entry. Significant or life-threatening myelosuppression may be managed with growth factor support including G-CSF, GM-CSF and platelet growth factors and erythropoietin/darbopoetin/blood transfusion according to institutional standard of care, American Society of Clinical Oncology (ASCO) Practice Guidelines, and/or NCCN Practice Guidelines.

### **5.6.4 Radiation Treatment**

If clinically indicated, palliative radiation therapy to non-target lesions is permitted but interruption of study drug is not required based on preclinical data and limited clinical observations. Treatment with selinexor shall not be discontinued solely due to palliative radiation.

### **5.6.5 Prohibited Concomitant medications**

Erythropoietin and growth factors are not permitted to be used prophylactically in cycle 1 but allowed if needed in cycle 2 and onwards. However, these can be used therapeutically throughout the study (see section 5.6.3 above).

### **5.6.6 Drugs undergoing Glutathione conjugation**

The primary metabolism of selinexor in vitro and in vivo appears to be inactivation by glutathione conjugation. In vitro studies using human liver microsomes confirm in vivo findings that selinexor undergoes minimal CYP450 metabolism. Therefore, administration of selinexor with drugs that undergo substantial glutathione conjugation should be minimized. These drugs include acetaminophen (paracetamol), which should be avoided 2 hours before and four hours after selinexor dosing. Studies of selinexor in combination with acetaminophen are ongoing in separate protocols. It should also be noted that ethanol ingestion is associated with glutathione depletion, therefore use of products containing ethanol should be minimized or avoided on selinexor dosing days.

### **5.6.7 Strong CYP3A4 inducers**

Avoid the concomitant use of strong CYP3A4 inducers (e.g., dexamethasone, phenytoin, carbamazepine, rifampin, rifabutin, rifapentine, phenobarbital) as they make decrease the systemic exposure to sorafenib.

- Other restrictions and precautions:
  - Alcohol: Ethanol should be avoided on selinexor dosing days as it may compete for glutathione-mediated metabolism.
  - Fasting: Patients on the selinexor arm should maintain an adequate diet.
  - Medications: Acetaminophen (paracetamol, Tylenol) and products containing acetaminophen (paracetamol) should be avoided 2 hours before and 2 hours after dosing with selinexor as it may compete with glutathione mediated metabolism.
  - Diet: There are no dietary restrictions on this study. Patients on the selinexor arm should maintain adequate caloric and fluid intake.

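### Dexamethasone is required with every selinexor dose in Section 5.6.1, optional in 5.5 and to be avoided in 5.6.7, so the three sections cannot all be followed

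*Combined protocol and SAP*

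**What the plan says.** Three sections of the combined protocol and SAP give dexamethasone three different standings.

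- **Section 5.6.1**, under the heading "Required Concomitant/Supportive Care Medications", states: "Oral dexamethasone (4 mg) will be given to all patients with each dose of selinexor". It permits higher doses for short periods, up to 40 mg per week.
- **Section 5.5** makes only the 5-HT3 antagonist compulsory. Beyond that, acid suppression, anti-emetics "and other treatments may be administered as described below", and the list that follows includes: "Glucocorticoids: dexamethasone (4-12 mg) or equivalent glucocorticoid (e.g., prednisone 10-20 mg) on days of, and 1 day after, selinexor dosing may improve appetite". The same 40 mg weekly ceiling applies.
- **Section 5.6.7** opens: "Avoid the concomitant use of strong CYP3A4 inducers (e.g., dexamethasone" and goes on to other drugs. The reason it gives is that such inducers may "decrease the systemic exposure to sorafenib".

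The selinexor toxicity table in Section 5.2.2 adds a fourth position. For fatigue, anorexia and nausea it suggests considering 4-8 mg of dexamethasone on the day after selinexor, as though the patient were not already taking it.

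**The concern.** An instruction to give a drug to everyone and an instruction to avoid it cannot both be carried out. The drug in question bears on both things this trial measures.

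- **Tolerability.** Section 5.6.1 says dexamethasone improves appetite and reduces nausea, vomiting and fatigue. Section 3.4 counts Grade 3 nausea/vomiting and Grade 3 fatigue as dose-limiting only if they outlast a set number of days under optimal supportive medication. If the standing of dexamethasone is undefined, part of the DLT standard is undefined too.
- **Exposure.** On the protocol's own account in 5.6.7, the drug may reduce exposure to sorafenib. CRc and toxicity of the combination are the outcomes monitored in phase II (Section 11.2).

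If different treating physicians follow different sections, the DLT, toxicity and CRc counts would mix patients on different regimens.

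**Working it through.** The plan states no figure on this point, so the check sets the instructions side by side, looks for text that reconciles them, and counts how often they collide.

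**Step 1. Side by side**

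| Section | Standing of dexamethasone | Dose and timing |
|---|---|---|
| 5.6.1 | Required for all patients | 4 mg with each selinexor dose (plus or minus one day after), up to 40 mg per week |
| 5.5 | Permitted | 4-12 mg or equivalent on the dosing day and the day after, up to 40 mg per week |
| 5.2.2 toxicity table | To be considered once toxicity appears | 4-8 mg on the day after |
| 5.6.7 | To be avoided | No dose or duration threshold |

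Giving 4 mg with each selinexor dose satisfies 5.6.1 and falls within what 5.5 allows. These two differ in standing and dose range but do not exclude each other. It is 5.6.7 that makes the set impossible to follow.

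**Step 2. Do the drugs overlap in time?** Section 5.1.1 gives sorafenib twice daily without planned interruption from cycle 1 day 1. Every selinexor day is therefore a sorafenib day unless sorafenib is being held for toxicity.

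**Step 3. How often?** Section 5.1.1 gives selinexor twice weekly for 3 weeks of each 28-day cycle:

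2 doses per week x 3 weeks = 6 doses per cycle.

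Section 5.6.1 thus calls for at least 6 dexamethasone administrations in a full cycle, all during sorafenib. Section 5.1.1.5 requires at least 4 selinexor doses in cycle 1 for DLT evaluability, so each DLT-evaluable patient meets the conflict 4 to 6 times inside the DLT window, unless sorafenib is held on some of those days.

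**Step 4. How far apart are the readings?** Dexamethasone per selinexor week:

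- 5.6.7 followed: 0 mg.
- 5.6.1 at its stated dose, once per selinexor dose: 2 x 4 = 8 mg.
- 5.5 if used on both days: 4 days x 4 mg = 16 mg at the low end. The high end is 4 x 12 = 48 mg, which the ceiling cuts to 40 mg.

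A patient could receive anything from 0 to 40 mg in a dosing week and be consistent with one of the sections.

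**Step 5. Does other text reconcile them?**

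- Section 5.6.2 permits supportive medication in general terms but does not mention inducers or dexamethasone.
- Section 4.2.6 has an exception for drugs critical to the patient, but for strong CYP3A4 inhibitors only.
- Section 5.6.5, on prohibited medication, does not name dexamethasone in either direction.
- Section 5.6.7 has no carve-out for the co-medication in 5.6.1.

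**Step 6. Could the effect be examined afterwards?** Section 7.2.6 keeps concomitant medication off the case report form, apart from first-cycle hydroxyurea. The planned samples (Sections 6.1-6.3, 7.1.10 and 7.2.8) include no sorafenib concentration. The trial dataset would show neither who received dexamethasone nor what sorafenib exposure resulted.

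**The case against.** The best case for leaving the text alone is that a sensible reader would follow 5.6.1. It is the specific instruction, with a named drug, dose and timing under a heading that says it is required. Section 5.6.7 is a class precaution that says avoid rather than prohibit, and the prohibited list in 5.6.5 does not include dexamethasone. The trial runs at one institution (Section 3.1), study-drug prescriptions come only from its own physicians (7.2.9), and changes to dose or schedule need its approval. If 5.6.1 is applied uniformly, the MTD and CRc simply describe the combination given with dexamethasone, and nothing is mixed. Dexamethasone use would also remain in each patient's medication record, which is retrievable for at most 52 patients.

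Much of this stands as a limit on likelihood. Pooling of differently treated patients is a risk, not something the documents show. The conflict that binds is 5.6.1 against 5.6.7, and 5.5 is a secondary misalignment.

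It does not remove the contradiction. The plan nowhere says that 5.6.1 takes precedence, and the softer word still cannot coexist with an unqualified requirement in all patients. Local physicians share care under Section 7.2 and would receive the treatment schema. Source records allow a retrospective chart search but do not put the variable in the analysis dataset.

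**Conclusion.** The concern holds. Sections 5.5, 5.6.1 and 5.6.7 cannot all be followed, and the documents contain nothing that reconciles them. The conflict reaches every patient, at up to 6 selinexor doses per cycle.

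The consequence for the results is less certain. The documents give no figure for the effect of intermittent dexamethasone on sorafenib exposure, so any effect on the MTD, toxicity or CRc cannot be sized. The phase I part is where a small difference would matter most. With up to 12 patients and a 3+3 rule (Sections 3.3 and 11.1), a single DLT turns an escalation into an expansion to 6 patients, and a second shows that the MTD has been exceeded.

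This rests on two assumptions: that avoid in 5.6.7 carries its ordinary meaning, and that sorafenib is being taken on selinexor days as scheduled. The correction should be made. Which instruction is clinically right is not a matter for this review.

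**What to change.** Reconcile Sections 5.5, 5.6.1 and 5.6.7 into one statement of whether dexamethasone is required, optional or to be avoided, with its dose, timing and any exception, and cross-refer to it from each section. Align the toxicity table in 5.2.2 with it. The sponsor and investigator must decide which instruction applies.

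If dexamethasone stays as a study-wide co-medication, amend 7.2.6 so that the dose given is entered on the case report form and DLTs, toxicity and CRc can be read alongside it. Section 3.4 should then refer to the reconciled statement when it speaks of optimal supportive medication.

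The cost is amendment wording, plus one CRF field if the drug is kept. The sample size, stopping boundaries and analyses do not change.

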## 6.0 CORRELATIVE/SPECIAL STUDIES (Optional)

### 6.1 Effect of MAPK, AKT signaling and apoptosis induction

The timetable for collection of peripheral blood will be as defined in section 7.2 below.

Vectra testing will be done for p53, survivin, FLT3, pPI3K, pAKT, pERK. Reverse phase protein assay (RPPA) will be utilized to assess activation of FLT3, MAPK, AKT (via detection of phosphorylated FLT3, ERK, pS6, p4EBP1 and pAKT). We will analyze induction of apoptosis in AML stem cells by 3-color flow cytometry assay (CD34/annexin V/CMXRos) established in [name] laboratory. RT-PCR analysis on selected markers will be done only on bone marrow samples.

Peripheral blood for these studies (Vectra, 3-color flow, RPPA) will be collected prior to the first dose of selinexor (baseline: day 1) in cycle 1, 24 (+/- 4) hours post the first dose of selinexor in cycle 1, cycle 1 day 28 (+/- 7 days), and at progression/relapse (if available). Bone marrow samples for studies (Vectra, 3-color flow, RPPA, PCR) will be collected at baseline (within the last 7 days preceding the first dose of selinexor), cycle 1 day 28 (+/- 7 days), and at progression/relapse (if available). Correlative studies and biomarker evaluation will be performed by [name] lab.

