### **1.3 Exploratory Objectives**

1. To evaluate the response rate, EFS and OS in FLT3 mutated/NPM1 wild-type patients versus FLT3 mutated/NPM1 mutated versus FLT3 wild-type/NPM1 mutated patients treated with the combination of selinexor and sorafenib.
2. Quantitative changes of FLT3-ITD and –D835 allelic burden with time in patients treated with the combination of selinexor and sorafenib.
3. To evaluate the extent of pharmacodynamics biomarker (such as p-FLT3, p-p70S6K, pERK) inhibition and the induction of apoptosis in the bone marrow and peripheral blasts following treatment with the combination of selinexor and sorafenib.
4. To investigate possible relationships between selinexor and other baseline gene expression signatures and clinical response.
5. To store and/or analyze surplus blood or tissue including bone marrow, if available, for potential future exploratory research into factors that may influence development of AML and/or response to selinexor (where response is defined broadly to include efficacy, tolerability or safety).
6. To evaluate the pharmacodynamic effects of treatment on induction/inhibition of XPO1 using qRT-PCR and on plasma protein/cytokine levels.

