**Table 3: Dosing schema**

Dose level	Sorafenib (in mg)	Selinexor (in mg) on days 1 and 3 of weeks 1-3 of each 4 week cycle
+1 (Target dose)	400 twice daily	100 mg* twice weekly
0 (Starting dose)	400 twice daily	80 mg twice weekly
-1	400 twice daily	60 mg twice weekly
-2	400 twice daily	40 mg twice weekly

\*not to exceed 70 mg/m^2 based on BSA

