## **5.0 TREATMENT PLAN:**

### **5.1 Schedule**

All patients will be registered through CORE/PDMS.

5.1.1 Selinexor will be administered orally twice a week (e.g. Monday/Wednesday or Tuesday/Thursday or Wednesday/Friday) for 3 weeks of a 28-day cycle. Selinexor will not be dosed the last week of the cycle (week 4). After initiation of sorafenib on cycle 1 day 1, sorafenib will be administered orally daily twice continuously for the duration of the study with no interruptions unless there are adverse events as described in Section 5.2 below. Sorafenib doses will be separated by intervals of approximately 12 hours (+/- 2 hours). Sorafenib will be administered without food, at least 1 hour before or 2 hours after eating. If a dose is missed, the

next dose will not be increased to account for missing a dose. The patient will take the next regular dose at the scheduled time. Patients will receive one cycle of therapy every 28 days (+/- 7 days).

On the day when both drugs, Selinexor and Sorafenib, will be administered:

- Selinexor needs to be taken with food.
- Sorafenib should not be taken with food. Therefore, patient should take Sorafenib at least 1 hour before eating or 2 hours after eating.

**5.1.1.1** Cycles may be started early (but not earlier than day 21) for patients with active disease if judged in the best interest of the patient.

\*For the phase I, DLT defining period is 28 days. As such, cycle 2 should not be started before 28 days for the patients being treated on the phase I cohort to allow for adequate evaluation of DLTs.

**5.1.1.2** Subsequent cycles may be delayed for recovery of toxicity or other medical conditions. Delays in start of subsequent cycles greater than 8 weeks will be acceptable only for patients who are deriving clinical benefit and after discussion with the principal investigator and the sponsor of potential risk/benefit ratio and complete documentation of the degree of clinical benefit and reason for continuation on this regimen.

**5.1.1.3** In instances where one drug has to be discontinued transiently because of safety, the administration of the other drug may continue as scheduled. If the drug that is held can resume at a later time, no doses will be made up and the administration will follow the originally defined schedule calendar according to the drug that was continued.

**5.1.1.4** For patients who discontinue therapy, the reason for treatment discontinuation will be documented.

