### 11.3 Statistical Analysis Plan

All patients who received any dose of the study agent will be included in the analysis for efficacy and safety. Demographic/clinical characteristics (including duration of response) and safety data of the patients will be summarized using descriptive statistics such as mean, standard deviation, median and range. For the primary efficacy analysis, we will estimate the ORR for the combination treatment, along with the 95% confidence interval. In addition, we will estimate composite CRc rate, partial response and marrow clearance rate within 3 months by FLT3 mutation. Patients who drop out of the study before completing all the cycles will be treated as “failures” for the primary analysis. ORR during the study period will also be presented with the 95% confidence interval. The association between ORR and patient’s clinical characteristics will be examined by Wilcoxon’s rank sum test or Fisher’s exact test, as appropriate. Toxicity type, severity and attribution will be summarized for each patient using frequency tables.

The distribution of time-to-event endpoints (DFS and OS) including overall survival and progression free survival will be estimated using the method of Kaplan and Meier. Comparisons of time-to-event endpoints by important subgroups will be made using the log-rank tests. Paired t-tests will be used to determine the immunological and molecular changes in the peripheral blood and bone marrow from baseline to the time of response, and to the time of disease progression.

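### The day-1 blood PD baseline is not protected from the first sorafenib dose, day-28 samples mix selinexor exposure states, and the paired tests in 11.3 do not match the sampling times

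*Combined protocol and SAP*

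**What the plan says.** Exploratory objective 3 (section 1.3) covers inhibition of markers such as p-FLT3, p-p70S6K and pERK, and "the induction of apoptosis in the bone marrow and peripheral blasts following treatment with the combination of selinexor and sorafenib". Objective 6 covers XPO1 and plasma proteins/cytokines.

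Sampling (sections 6.1 to 6.3, 7.1.10, 7.2.8):
- Blood for flow cytometry, RPPA and Vectra is "collected prior to the first dose of selinexor (baseline: day 1) in cycle 1", then at 24 ± 4 hours after that dose, at cycle 1 day 28 ± 7, and at progression or relapse if available.
- Blood for XPO1 and cytokines is taken before the first selinexor dose and 4 ± 1 hours after it, on cycle 1 day 1 only.
- Marrow is taken at baseline, at day 28 ± 7, and at progression or relapse if available.

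Dosing: Table 3 gives "Selinexor (in mg) on days 1 and 3 of weeks 1-3 of each 4 week cycle". Section 5.1 says: "After initiation of sorafenib on cycle 1 day 1, sorafenib will be administered orally daily twice continuously for the duration of the study". Selinexor goes with food. For sorafenib on a day with both drugs, "patient should take Sorafenib at least 1 hour before eating or 2 hours after eating".

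Analysis: section 11.3 plans paired t-tests of immunological and molecular changes "from baseline to the time of response, and to the time of disease progression".

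**The concern.** Three links between dosing, sampling and analysis are loose.

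1. The day-1 blood baseline is tied to one drug although two start that day. Section 2.1 describes sorafenib as potent against FLT3 and the Raf/ERK/MAPK pathway, which p-FLT3 and pERK read. A baseline drawn after sorafenib is already partly treated, and the change measured from it understates the inhibition.
2. The day-28 sample has a two-week window around the point where cycle 2 selinexor may start. Some patients will have been off selinexor for well over a week and others will just have been re-dosed. Nothing in the plan separates them.
3. The stated tests are tied to clinical events, while the early samples are tied to the clock. The samples closest to the first doses have no stated analysis.

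At stake is whether the PD results can be interpreted against objectives 3 and 6. No primary, secondary, safety or stopping decision depends on them.

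**Working it through.** The plan states no interval or effect size here, so there is no figure of its own to reproduce. The checks are day arithmetic and a comparison of sections.

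**Order of events on day 1.** Selinexor is taken within 30 minutes of solid food (5.4.4). Sorafenib is taken at least 1 hour before eating or 2 hours after (5.1.1). One permitted sequence is sorafenib, then the blood draw, then the meal with selinexor. Sections 6.1, 6.2, 6.3, 7.1.10 and 7.2.8 all name only the first selinexor dose, so this sequence meets every one of them.

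**Direction of the bias.** Let I be the true inhibition from an untreated baseline and s the suppression already present when the baseline is drawn. Measured inhibition = 1 − (1 − I)/(1 − s). The documents give no s. As an illustration only, with I = 85% assumed:
- s = 0: 1 − 0.15/1.00 = 85%
- s = 25%: 1 − 0.15/0.75 = 80%
- s = 50%: 1 − 0.15/0.50 = 70%

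The direction is fixed as long as s is below I. The size is not known.

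**Selinexor to day-28 sample.** Dosing days are 7w + 1 and 7w + 3 for w = 0, 1, 2, which gives days 1, 3, 8, 10, 15 and 17. The window is days 21 to 35. The interval is the sampling day minus the last selinexor day on or before it.

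| Cycle 2 start | Sample day 21 | Day 28 | Days 29 to 35 |
|---|---|---|---|
| Not before day 36 | 21 − 17 = 4 | 28 − 17 = 11 | 12 to 18 |
| Day 29 | 4 | 11 | 0 to 4 |
| Day 22 (early start, not in phase I) | 4 | 28 − 24 = 4 | 0 to 4 |

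So 11 days is the nominal value and 0 to 18 days the range, with all six cycle 1 doses taken on the Table 3 days. Sorafenib is continuous throughout.

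**24-hour blood.** With the first sorafenib dose between 1 hour before and 2 hours after selinexor, and 12-hour spacing, 2 to 3 sorafenib doses precede the 20-to-28-hour draw. This sample is under both drugs.

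**Tests against samples.**
- XPO1 and cytokines are drawn only on cycle 1 day 1. Neither contrast in 11.3 can be formed for them.
- The 24-hour blood belongs to neither contrast.
- Response counts at any time in the first three cycles (8.8, 11.2), and clinical marrow is scheduled at day 28 of cycle 3 (7.2.5). Section 6.1 schedules PD samples only at cycle 1 day 28 and at progression or relapse. A response first seen later has no scheduled PD sample.

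**The case against.** The other side has several good arguments.

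- **Intent is clear.** Section 7.1.10 lists the day-1 blood as pretreatment, section 4.0 wants baseline evaluations before the first dose of study drug, and 7.1 times pretreatment studies to that dose. This shows what was meant. It does not override the sentence that site staff will follow, which names selinexor alone.
- **The marrow baseline is safe.** Sections 7.1.10 and 7.2.8 place it within 7 days before study initiation. This stands, so the baseline problem concerns blood only.
- **Tying PD marrow to the clinical aspirate spares an extra procedure.** This is a legitimate choice. It argues for labelling exposure at day 28, not for moving the marrow.
- **Some molecular data exist at later responses.** FLT3 PCR is run on the clinical marrows in 7.2.5, and 7.2.8 gives the PD marrow day without a cycle number. But 6.1 makes it cycle 1, and the blood schedule does too.

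A reader might also infer more than the documents support:

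- That inhibition by the combination cannot be derived at all. The 24-hour blood is under both drugs and gives the acute combined change in peripheral blasts if the baseline precedes both. The marrow pair gives a baseline-to-day-28 change, and a progression marrow may also fall on treatment.
- That day-28 samples can show nothing of selinexor because the drug has cleared. The documents give no human half-life, describe slowly reversible binding (2.2), and say the effect of both drugs may be delayed by up to 4 weeks (5.6.2).
- That the response contrast is capped at 7 and 4 pairs. Those are 0.35 × 20 and 0.20 × 20, the expected CRc counts at the target rates in the FLT3 inhibitor naive and failure cohorts. They are not maxima. Section 8.0 defines responders more widely, and up to 12 phase I patients are not counted.

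**Conclusion.** The concern holds as a minor point with three parts.

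1. The day-1 blood baseline may follow the first sorafenib dose, which biases measured p-FLT3 and pERK inhibition toward zero. The size is unknown; it depends on how many patients take sorafenib first and how quickly it acts, and the documents give neither.
2. The only fixed-time on-treatment marrow is nominally 11 days after selinexor, with a range of 0 to 18 days. Pooled day-28 values therefore mix exposure states, and no marrow sample is timed to recent dosing with both drugs. The day-28 blood has the same spread.
3. The tests in 11.3 leave out the 4-hour and 24-hour samples and rely on a response sample that is not scheduled after cycle 1 day 28.

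The intervals assume dosing as in Table 3. The samples are optional, missed ones are not deviations, and the objectives are exploratory.

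**What to change.** 1. In 6.1, 6.2, 6.3, 7.1.10 and 7.2.8, require the baseline sample before the first dose of either study drug. For XPO1 and cytokines this is for consistency; the bias argument rests on FLT3 and Raf/ERK.
2. In 11.3, specify paired contrasts at the scheduled times, in all patients with both samples:
   - pre-dose versus 4 hours for XPO1 and cytokines;
   - pre-dose versus 24 hours, and versus day 28, for blood flow cytometry, RPPA and Vectra;
   - baseline versus day 28 for marrow.

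   Keep response and progression as secondary contrasts.
3. Record the time since the last dose of each drug at every PD sample. Report day-28 samples taken before and after the first cycle 2 selinexor dose separately.

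The cost is a few sentences and two time fields per sample. The number of samples, the dosing and the clinical marrow schedule do not change. Splitting the day-28 samples makes each group smaller. Moving the day-28 blood draw closer to a selinexor dose is optional: it would improve timing but lose the blood value paired with the marrow.
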